Appendix A

LezParlay Promotional Flyer and Social Media Ads

Figure A6. Flyer to be distributed at local LBQ events in Los Angeles, CA along with promotional branded items (chapsticks, coffee mugs, temporary tattoos)

Figure A1. Lesbian-identity tailored HER Social App campaign promo video to be pinned to the top of HER newsfeed area. Viewable at <https://www.youtube.com/watch?v=x9Y7oobC1Zw>

[figure not shown]

Figure A2. HER Social App banner smartphone notification to be received by users in Los Angeles, New York City, and Atlanta

[figure not shown]

Figure A3. LezParlay multi-image carousel ad mockups for Facebook and Instagram

 **LezParlay**
Sponsored · 

Find out how your health, drinking, and relationship history really compare to other women your age while increasing LBQ visibility, challenging stereotypes, & competing for cash in our online LezParlay competition! IT'S FREE.

LEZPARLAYLA.COM

[figure not shown]
Compete against LBQ women in their 40s & 50s

cats. lesbian bed death. flannel shirts. co-dependence....

 Like  Comment  Share

 **LezParlay**
Sponsored · 

Got 2 minutes? Round 2 of the competition closes soon and \$300 is up for grabs... 800 LBQ players and growing, you don't wanna miss this!

tats, flannel, & gold stars

 Sign Up

get your bets in before it's too

 Like  Comment  Share

Figure A4. Additional drafts of Facebook & Instagram ads.

Desktop

Stereotype Challenge | for Lesbian, Bi, & Queer Women

Ad www.lezparlayla.com

Test your perceptions. Find out how your health, relationships, & sex life really compare. 4 age-groups: Play in your 20s, 30s, 40s, or 50s. \$10,000 in cash prizes & 100% free!

Learn About the Cause

[Learn more](#)

[Find out why we created this](#)

Find Out How it Works

[Get the details](#)

[View the FAQs](#)

Mobile

Stereotype Challenge | for Lesbian, Bi, & Queer Women | Compete Online for Free

Ad www.lezparlayla.com

Test your perceptions. Find out how your health, relationships, & sex life really compare. 4 age-groups: Play in your 20s, 30s, 40s, or 50s. \$10,000 in cash prizes & 100% free!

Learn About the Cause

Find Out How it Works

[figure not shown]
Register & Play Round 1

Figure A5. Google Search Ad Preview targeting searches of terms and phrases including “lesbian chat”, “lesbian dating site” “queer dating” “bisexual dating” “LGBTQ pride events” “queer chat” “lesbian bar” “queer nightclub” “lesbian party” “queer party”

When the round closes we'll text you a link to view your detailed, personalized results. Find out the accuracy of your guesses, the points you won and lost, how your responses compare to other lesbian, bi, and queer players, any stereotypes shattered or confirmed, and the winner of the cash prize.

APPENDIX C

Norm questions to be featured in intervention rounds or potentially featured as control/filler questions in LezParlay Rounds

- Parallel Questions will also ask participants to report their own corresponding behavior/attitude/experience
- All questions will pipe the sexual identity (lesbian, bisexual, queer) and age-group (20s, 30s, 40s, 50s) of the user
- Some question topics and questions to appear in rounds will be voted on by players.
- Players can also submit their own questions to be voted on and potentially featured in some rounds.
- If any top voted user-submitted materially differ from those submitted in this exhaustive potential question list, we will submit an addendum to the IRB and get approval before any are featured in a round.

Alcohol Use Questions (Round 3 & Replay Bonus in Round 7)

During the past 2 months, on average, how many days per week did the Typical Lesbian drink alcohol?

- 0
- 1
- 2
- 3
- 4
- 5
- 6
- 7

During the past 2 months, on average, how many drinks did the Typical Lesbian have each time she drank?

- 0
- 1
- 2
- 3
- 4
- 5
- 6
- 7
- 8
- 9

10 or more

On the day she drank the MOST during the past 2 months, how many drinks did the Typical Lesbian have?

0

1

2

3

4

5

6

7

8

9

10

11

12 or more

HAD A HANGOVER OR ILLNESS

HAD PROBLEMS WITH FRIENDS OR FAMILY

GOT IN A PHYSICAL OR VERBAL FIGHT

PERFORMED POORLY AT WORK/SCHOOL

HAD PROBLEMS WITH GF/PARTNER

HAD PROBLEMS WITH MONEY

MISSED A SOCIAL ENGAGEMENT OR
EVENT

HAD AN UNWANTED OR REGRETTABLE
SEXUAL EXPERIENCE

During the past 2 months, how many of the 8 things above has the typical lesbian experienced due to drinking/partying?

0

1

2

3

4

5

6

7

Stigma Questions (Round 3 & Replay Bonus in Round 7)

During the past 2 months, what % of lesbians have been physically assaulted due to their sexual identity?
0% ----- 100%

During the past 2 months, what % of lesbians have been verbally harassed or threatened online or in person due to their sexual identity?
0% ----- 100%

During the past 2 months, what % of lesbians have overheard negative LGBTQ-related comments, jokes, or slurs?
0% ----- 100%

During the past 2 months, what % of lesbians have felt unwelcome or uncomfortable in a public place (gym locker room, store, restaurant, etc., due to their sexual identity?
0% ----- 100%

Coping Behaviors (Round 4)

When experiencing stress & stigma during the past month, what % of the time did the typical lesbian cope by drinking alcohol?
0% ----- 100%

When experiencing stress & stigma during the past month, what % of the time did the typical lesbian cope by taking a drug?
0% ----- 100%

When experiencing stress & stigma during the past month, what % of the time did the typical lesbian cope by meditating, using relaxation techniques, or exercising?
0% ----- 100%

When experiencing stress & stigma during the past month, what % of the time did the typical lesbian cope by talking to a close friend, family member, or mental health professional?
0% ----- 100%

How acceptable or unacceptable does the Typical lesbian find using alcohol and drugs to cope with problems or negative emotions?
Extremely Unacceptable ----- Extremely Acceptable

How acceptable or unacceptable does the Typical Lesbian find seeing a mental health professional for help coping with problems or negative emotions?
Extremely Unacceptable ----- Extremely Acceptable

Health related questions to be featured in the final round for norm documentation purposes

In the past month, how many days per week did the Typical Lesbian exercise for 45 minutes or longer (e.g., run, cycle, spin, lift weights, swim, etc.)?

- 0
- 1
- 2
- 3
- 4
- 5

- 6
- 7

How long ago was the Typical lesbian's last routine wellness check-up?

- less than 5 months ago
- 6-11 months
- 1 year
- 2 years
- 3 years
- 4 years
- 5 years or longer

How long has it been since the Typical Lesbian last had a pap test?

- 6 months or less
- 7-12 months
- 1.5 years
- 2 years
- 2.5 years
- 3 years or longer
- She has never had one!

What percent of typical Lesbians are "out" to their doctor?

0%-----%100

What percent of lesbians currently smoke cigarettes or vape?

0%-----%100

What percent of lesbians used to smoke but successfully quit?

0%-----%100

What percent of lesbian smokers, regret ever having started smoking?

0%-----%100

What percent of lesbians would NOT date a smoker?

0%-----%100

Potential non-health related control and filler questions to appear in rounds

How many uhaul (cohabitating) relationships has the typical lesbian had?

- 0
- 1
- 2
- 3
- 4
- 5
- 6
- 7
- 8
- 9
- 10 or more

How many ex-girlfriends has the typical lesbian in her 30s talked to in the past month?

- 0
- 1
- 2
- 3
- 4
- 5
- 6
- 7
- 8
- 9
- 10 or more

What percent of lesbians currently have 1 or more cats in their household?

0% ----- 100%

What percent of lesbians currently have 1 or more dogs in their household?

0% ----- 100%

What percent of lesbians like cats more than dogs?

0% ----- 100%

What percent of lesbians have rescued a pet?

0% ----- 100%

What percentage of lesbians see themselves living in their current state for the rest of their lives?
0% ----- 100%

What percentage of lesbians see themselves getting married or are already married?
0% ----- 100%

What percentage of lesbians see themselves raising children or are already raising children?
0% ----- 100%

What percentage of lesbians want to give birth or already have?
0% ----- 100%

What percentage of lesbians own a pair of Birkenstocks?
0% ----- 100%

What percentage of lesbians have worn a beanie or a fedora during the past month?
0% ----- 100%

What percentage of lesbians have worn a flannel shirt in the past month?
0% ----- 100%

What percentage of lesbians own a black leather jacket?
0% ----- 100%

What percentage of lesbians have short hair?
0% ----- 100%

How many tattoos does the typical lesbian have?

- 0
- 1
- 2
- 3
- 4
- 5
- 6
- 7
- 8
- 9
- 10 or more

How many flannel shirts does the typical lesbian own?

- 0
- 1
- 2

- 3
- 4
- 5
- 6
- 7
- 8
- 9
- 10 or more

How many piercings does the typical lesbian have?

- 0
- 1
- 2
- 3
- 4
- 5
- 6
- 7
- 8 or more

How many times has the Typical Lesbian been in love?

- 0
- 1
- 2
- 3
- 4
- 5
- 6
- 7
- 8 or more

What percent of lesbians have had a relationship with someone they met online?

0%-----%100

How acceptable or unacceptable would the typical lesbian find only seeing a new love interest twice a week for the first few months of dating?

- Very Unacceptable
- Moderately Unacceptable
- Slightly Unacceptable

- Neither Unacceptable or Acceptable
- Slightly Acceptable
- Moderately Acceptable
- Very Acceptable

How acceptable or unacceptable would the typical lesbian find waiting at least 12 months to move in with a new girlfriend?

- Very Unacceptable
- Moderately Unacceptable
- Slightly Unacceptable
- Neither Unacceptable or Acceptable
- Slightly Acceptable
- Moderately Acceptable
- Very Acceptable

How acceptable or unacceptable would the typical lesbian find getting to know a love interest for 4 weeks before having sex with her?

- Very Unacceptable
- Moderately Unacceptable
- Slightly Unacceptable
- Neither Unacceptable or Acceptable
- Slightly Acceptable
- Moderately Acceptable
- Very Acceptable

Sex

How many female sexual partners has the Typical Lesbian had?

1	13
2	14
3	15
4	16
5	17
6	18
7	19
8	20 or more
9	
10	
11	
12	

During the past month, on average, how many days per week did the Typical Lesbian have sex?

- 0
- 1
- 2

- 3
- 4
- 5
- 6
- 7

During the past month, how long in duration was the Typical Lesbian's average sexual encounter?

- 10 minutes or less
- 11-20 minutes
- 21-30 minutes
- 31-40 minutes
- 41-50 minutes
- 51-60 minutes
- 61-70 minutes
- 71 minutes or more

What percent of lesbians have experienced "lesbian bed death" or an extremely low frequency of sex in a serious relationship?
0%-----%100

What percent of lesbians scissor?
0%-----%100

What percent of lesbians have all 3 of the following social media accounts: Facebook, Twitter, Instagram?
0%-----%100

What percent of lesbians have used HER social app?
0%-----%100

What percent of lesbians read IntoMore or Autostraddle?
0%-----%100

How many seasons of the LWord has the typical lesbian seen?
 0

- 1
- 2
- 3
- 4
- 5

6

How many times per day does the typical lesbian check Facebook?

0

1

2

3

4

5

6

7 or more

How many times per day does the typical lesbian check Instagram?

0

1

2

3

4

5

6

7 or more

How many times per day does the typical lesbian check Twitter?

0

1

2

3

4

5

6

7 or more

What percent of lesbians voted in the midterm election?
0%-----%100

What percent of lesbians have attended a political march or protest during the past year?
0%-----%100

What percent of lesbians consider themselves to be a feminist?
0%-----%100

What percent of lesbians hate men?
0%-----%100

What percent of lesbians have negative attitudes toward transwomen?
0%-----%100

What percent of lesbians are good at household repairs?
0%-----%100

What percent of lesbians have visited a home improvement store in the past month?
0%-----%100

What percent of lesbians consider themselves to be athletic?
0%-----%100

What percent of lesbians played a varsity sport in high school or college?
0%-----%100

What percent of lesbians own a toolbox?
0%-----%100

What percent of lesbians would change their own flat tire rather than calling AAA?
0%-----%100

What percent of lesbians are vegan or vegetarian?
0%-----%100

What percent of lesbians have been confused for sisters while out with a significant other?
0%-----%100

What percent of lesbians have been told their sexual identity is “just a phase”
0%-----%100

What percent of lesbians have seduced a straight woman?
0%-----%100

What percent of lesbians have had a threesome?
0%-----%100

What percent of lesbians have been in a polyamorous relationship?
0%-----%100

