Multiple strategies will be employed to recruit approximately 1200 lesbian, bisexual, and queer identified women residing in the United States to take part in the online LezParlay competition. Topics in the game will change from month to month and will feature stigma-coping behaviors and alcohol use, among other topics related to familiar lesbian and queer stereotypes (e.g., relationships, sex, identity, money, stress, and future plans). Over 8 monthly rounds of play, players will receive PNF on different topics and compete for cash prizes as they test the accuracy of their peer perceptions and discover how their own attitudes and behaviors compare to actual group norms. Importantly, in Round 3, when alcohol use is first assessed as a topic, a sub-sample of 500 players who report moderate drinking will be invited to participate in a LezParlay evaluation study. Participants who elect to take part in the study will be randomized to receive either PNF on alcohol use + coping behaviors, PNF on alcohol use + control topics, or PNF on control topics in subsequent rounds of the game. These study participants will be incentivized for playing remaining rounds and completing a follow-up survey about their experiences. Analysis of LezParlay efficacy will focus on longitudinal changes in alcohol use and coping behaviors associated with condition assignment and subsequent receipt of PNF among study participants. Analysis of feasibility associated with the gamified LezParlay format will focus on acceptability ratings and other feedback gathered from trial participants as well as basic application usage among the pool of players who elect to take part in the competition but do not participate in the study, and thus, are not incentivized for their completion of rounds.

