- 1) Report having had 3+ drinks on one occasion during the past 2 months OR drinking alcohol 3+ times per week during the past 2 months in response to a Round 3 Alcohol use questions
- 2) Review and Accept the Evaluation Study Informed Consent page
- 3) Have taken part in at least 1 previous round of the competition

Two questions about alcohol use in the third round of the game will act as a screening item for the Evaluation study. Specifically, participants will be quota sampled by Qualtrics in response to a Round 2 question about the maximum number of drinks consumed on one occasion during the past month. The first 150 drinkers in each age-group (i.e., 20s, 30s, 40s, 50s) who provide an answer equal to or above 3 drinks in response to this question will be invited to become an official tester in a study evaluating LezParlay. On screen text will explain that as a participant in this study they can help evaluate LezParlay by playing the next 5 rounds of the game and completing a follow-up survey about their experiences when the game is over. Further, study participants will be emailed a \$40 electronic gift card to compensate them for their time and they will still be eligible to compete for performance-based cash prizes awarded to the top scorers.

“Non-Evaluation Study participants” refer to players who register for LezParlay but either do not screen into the study or choose not to participate in the study. Non-Evaluation Study participants are not incentivized for round completion but may compete for several performance-based cash prizes awarded to the top scorers in each age-group. For these participants, LezParlay web app data analyzed for research purposes is limited to aggregated demographic data provided at registration, the number of

rounds played, number of logins, and number of screen views. Collection and analysis of this data is outlined in the web app's Terms of Service & Privacy Policy which ALL participants must review and accept at registration.

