
After viewing these results screens, participants have the option of beginning the next round or being reminded to complete it later. The participant experience and sequence of screens encountered in all rounds are the same as detailed above with 2 exceptions: Rounds 3 and 4, which are intervention rounds and Rounds 7 & 8 which include REPLAY BONUSES.

Intervention Rounds 3 and 4. We aim to recruit a minimum of 1200 LBQ women to sign up during the first 2 monthly rounds to ensure that meaningful and stable sexual identity- and age group-specific actual norms for drinking and coping behaviors can be delivered in intervention rounds 3 and 4. From this larger pool of players, 500 will be recruited to participate in a LezParlay evaluation study (RCT) during Round 3. Acting as baseline (T1) for the RCT, Round 3 will feature questions about alcohol use, stigma experiences, and a group of nonhealth-related control questions submitted by players. Upon submitting answers to alcohol-related questions in Round 3, players will be covertly screened for evaluation study eligibility based on their answers (i.e., number of drinking days per week and peak drinks on a single day during the past 2 months) as well as their geolocation and the number of previous rounds played. Those who have played at least one previous round, are in the United States, and report drinking alcohol on 3 or more days per week or having 3 or more drinks on their peak drinking occasion will be invited to take part in an evaluation study at the end of the round. Interested potential participants will advance to an informed consent screen that explains that the goal of the study is to evaluate the impact and format of detailed results received in LezParlay and gather player feedback to inform the next version of the competition. The information further detailed that participation in the evaluation study simply involves playing and viewing detailed results in subsequent rounds and completing a brief feedback survey at the end of the competition. Participants can earn up to US \$40 in electronic gift cards of their choice to play subsequent rounds and complete the feedback survey. Those who check a box indicating that they understood what the study participation entails and would like to participate will be welcomed into the study.

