Qualtrics Research Suite's automated randomizer will be used to randomize evaluation study participants to a PNF condition at the point of study enrollment in round 3. Randomization will determine the sequence of topics on which participants will receive detailed results across intervention rounds 3 and 4: alcohol+coping, alcohol+control, or control only. Members of the research team will be blinded to participant condition assignment, and the study participants will not be aware that any sort of randomization was taking place. Rather, like in other rounds, when detailed results are sent players will be prompted to choose among 3 animated, graphical doors to determine the topics on which they will view detailed results. Although the results topics will be truly determined via chance in most rounds of the competition, the doors of evaluation study participants will be fixed to open to their randomly assigned feedback topics regardless of the door they selected in rounds 3 and 4. Upon completing the feedback survey at the end of the competition, participants will be debriefed regarding the study's research questions and the fixed sequences of health or control feedback they were randomized to receive in rounds 3 and 4. See Appendix D for the Debriefing Statement.

Replay Bonus Rounds 7 and 8.

The last 2 rounds of the competition, 7 & 8, will feature new question topics as well as previously assessed REPLAY BONUS topics which will allow all players to boost their scores by placing very large bets on a topic they already received feedback on and very small bets for topic on which feedback has not yet been delivered. PNF will be delivered for the new topics assessed in each round but will not be repeated for REPLAY BONUS topics. Instead a single screen will reveal the points earned from REPLAY BONUSES. Importantly, answers to REPLAY BONUS questions in Round 7 among intervention study participants' will act as the 2 month post-intervention follow-up for the purpose of the evaluation study RCT.

Competition Conclusion

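### The drinking-frequency item offers only whole days per week, so it cannot resolve drinking below once a week, yet one 3-drink occasion in 2 months is enough to enter the trial

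*Protocol*

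**What the plan says.** Appendix C (Alcohol Use Questions, for Round 3 and the Round 7 replay) prints the frequency item as "During the past 2 months, on average, how many days per week did the Typical Lesbian drink alcohol", with the options 0, 1, 2, 3, 4, 5, 6 and 7. Nothing lies between 0 and 1, and no rounding instruction is given.

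The printed wording is the peer version. The introductory bullets add: "Parallel Questions will also ask participants to report their own corresponding behavior/attitude/experience". The own-report option list is not printed separately. Section 3 describes players guessing how others answered the same questions, so a common list is the natural reading, but it is an inference.

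Section 2 sets entry to the evaluation study as "Report having had 3+ drinks on one occasion during the past 2 months OR drinking alcohol 3+ times per week". Section 3 repeats the either/or form: "report drinking alcohol on 3 or more days per week or having 3 or more drinks on their peak drinking occasion". The peak criterion alone is therefore sufficient.

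On use of the answers, Section 1 states: "Analysis of LezParlay efficacy will focus on longitudinal changes in alcohol use and coping behaviors". Round 3 is baseline, and Section 3 says that "answers to REPLAY BONUS questions in Round 7 among intervention study participants' will act as the 2 month post-intervention follow-up". Section 3 also builds the feedback bar chart from the player's guess, her own answer and the average answer of other players.

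The same block of Appendix C has three further alcohol items: drinks per occasion ("During the past 2 months, on average, how many drinks did the Typical Lesbian have each time she drank"), peak drinks ("On the day she drank the MOST during the past 2 months, how many drinks did the Typical Lesbian have") and a count of alcohol-related consequences.

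**The concern.** The entry rule and the frequency scale do not match. The rule admits women who drink a few times in two months. The scale's smallest step is one day per week, which is 8 to 9 drinking days over the same period. A woman with a peak of 3 or more drinks may thus be recorded as drinking on 0 days per week, which is an inconsistent record. On that item she then has no room to improve.

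At stake is the sensitivity of one of the alcohol measures at both baseline and follow-up. Any weekly quantity formed as days times drinks per occasion would inherit the zero. The personal bar and the norm bar in the alcohol feedback come from the same coarse answers. This is not something an analysis plan can repair, because the response options determine what is collected.

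**Working it through.** The protocol gives no figure to reproduce here. The check converts drinking days to the unit of the item.

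**Inputs.** Look-back of 2 months and options 0 to 7 (Appendix C); peak of 3 or more drinks sufficient for entry (Sections 2 and 3). Assumption: 2 months = 61 days.

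**Formula.** Weeks = 61 / 7 = 8.71. Days per week = drinking days / 8.71.

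| Drinking days in 2 months | Days per week | Nearest option | Rounded down | Rounded up |
|---|---|---|---|---|
| 1 | 0.11 | 0 | 0 | 1 |
| 4 | 0.46 | 0 | 0 | 1 |
| 5 | 0.57 | 1 | 0 | 1 |
| 8 | 0.92 | 1 | 0 | 1 |
| 9 | 1.03 | 1 | 1 | 2 |
| 13 | 1.49 | 1 | 1 | 2 |
| 14 | 1.61 | 2 | 1 | 2 |

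**Sensitivity to the window.** With 60 to 62 days, 1 to 4 drinking days give 0.11 to 0.47 and the nearest option is still 0. With exactly 8 weeks, 4 / 8 = 0.5 is a tie, so only 1 to 3 days are clearly 0.

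**What each rounding habit does to a fall from 4 days to 1 (3 / 4 = 75% lower).**
- Nearest or downward: 0 to 0, not visible.
- Upward: 1 to 1, not visible. Only a fall to no drinking at all shows, as 1 to 0.

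**Above the floor (nearest rounding).** A fall from 13 days to 5 (8 / 13 = 62% lower) stays at 1. A rise from 5 to 13 also stays at 1. A change of a single day, from 14 to 13, registers as 2 to 1. Coarsening there hides some changes and magnifies others, in both directions.

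**Ceiling on what is lost.** A woman at the floor under nearest rounding can truly fall by at most about 0.46 days per week, even if she stops drinking.

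**Illustration of power on this item alone, with assumed inputs.** Take 500 / 3 ≈ 166 per arm, two-sided alpha 0.05 and 80% power. The detectable standardized difference is (1.960 + 0.842) × √(2 / 166) = 0.308. If a share f of women can show no change, the mean effect shrinks to (1 − f) × 0.308. Power is then about 71% at f = 10%, 61% at f = 20% and 50% at f = 30%. The protocol gives neither f nor alpha nor power. The sum also lets each affected woman otherwise contribute the full average effect, which the 0.46-day cap may not allow, and it holds the standard deviation fixed. It shows direction and is not an estimate of the loss.

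**The case against.** The strongest reply is that frequency is one of four alcohol items. A woman who enters by the peak route has a baseline peak of at least 3 by definition, so the item that admits her has room to fall. Drinks per occasion and consequences can fall too. This stands. A reader might infer that no reduction in alcohol use can register for these women; the protocol does not support that, and the limit applies to frequency and to products built on it.

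A reader might also infer that such women necessarily start at 0. That depends on rounding, which the protocol does not fix; a woman who knows that she drank may choose 1. This stands as well, but it does not rescue the item: under any consistent habit, a fall from 4 days to 1 is invisible.

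Three further objections stand:
- The protocol defines no days-times-drinks outcome and names no primary alcohol item, so harm to a weekly quantity is conditional on one being used.
- Coarsening also hides increases: a rise from 1 day to 4 stays at 0 under nearest rounding. A general pull toward no effect is therefore not shown, although women at 0 can register only increases.
- Distortion of the delivered norm is not shown. Under nearest rounding, 1 to 4 days move down to 0 while 5 to 8 move up to 1, and the net direction depends on a distribution that the protocol does not give.

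**Conclusion.** The point holds for the drinking-frequency item and any weekly quantity derived from it. The entry rule admits women whose drinking the 0-to-7 scale cannot resolve: 1 to 4 drinking days in about 61 days is 0.11 to 0.46 days per week. Under nearest rounding these women sit at 0 and cannot show a fall; under upward rounding only abstinence shows.

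This rests on two assumptions: that the own-report item shares the printed option list, and that the window is close to 60 to 62 days. The number of women affected is unknown, and their loss is capped at under half a day per week each. The protocol therefore does not support a claim that the trial's efficacy assessment is compromised. Severity is optional to minor, with moderate confidence. The reason to act is that the change is cheap before Round 3 and impossible to make good afterwards.

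**What to change.** Before Round 3, add response options below once a week to the own-report frequency item and to the matching peer-guess item, in both Round 3 and Round 7. For example: once in 2 months, once a month, 2 to 3 times a month. Convert to decimal days per week for the norm, the bar chart and the analysis. On 8.71 weeks these are 1 / 8.71 = 0.11, 2 / 8.71 = 0.23 and, at the midpoint of 4 to 6 days, 5 / 8.71 = 0.57. A fall from 4 days to 1 would then read as 0.57 to 0.11. The existing frequency cut for eligibility can be applied unchanged to the converted value. A count of drinking days in the past 2 months would serve equally, and would also remove the one-day steps above the floor.

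Align the days-per-week question in the Appendix D feedback survey with the same scale; its options are not shown in the text, so check first whether it needs changing.

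The cost is a longer option list, a decimal on the feedback chart and a small adjustment to scoring. Appendix B pays out for guesses close to the average and doubles the bet for exact ones, so closeness on this item must be redefined for the new scale.

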The ability to compete as a couple against other couples			
The ability to send other players a "wink" or "nod"			
The ability to message other players			

Did you find taking part in the competition to be beneficial to you at all?

No

Yes

[IF YES]

[figure not shown]

Great! Please use the text box below to briefly describe how the competition was beneficial for you

Do you any other ideas about how LezParlay might be improved?

What would you like to see be different in the next version?

Last thing, we promise! Now that the summer is ending,
please answer the 5 drinking questions a final time.

SINCE THE BEGINNING OF JULY, ON AVERAGE, HOW MANY DAYS PER WEEK
HAVE **YOU** DRANK?

SINCE THE BEGINNING OF JULY, ON AVERAGE, HOW MANY DRINKS HAVE **YOU** HAD EACH
DAY YOU DRANK?

SINCE THE BEGINNING OF JULY, ON THE DAY YOU DRANK THE MOST, HOW MANY DRINKS DID YOU HAVE?

0 1 2 3 4 5 6 7 8 9 10 11 12+

HAD A HANGOVER OR ILLNESS

GOT IN A PHYSICAL OR VERBAL FIGHT

HAD PROBLEMS WITH GF/PARTNER

MISSSED A SOCIAL ENGAGEMENT OR EVENT

HAD PROBLEMS WITH FRIENDS OR FAMILY

PERFORMED POORLY AT WORK/SCHOOL

HAD PROBLEMS WITH MONEY

HAD AN UNWANTED OR REGRETTABLE SEXUAL EXPERIENCE

SINCE THE BEGINNING OF JULY, HOW MANY OF THE 8 THINGS ABOVE HAVE YOU EXPERIENCED DUE TO DRINKING/PARTYING?

SINCE THE BEGINNING OF JULY, WHEN YOU'VE EXPERIENCED STIGMA OR NEGATIVE EMOTIONS WHAT % OF THE TIME DID YOU DRINK ALCOHOL IN AN EFFORT TO FEEL BETTER?

0 10 20 30 40 50 60 70 80 90 100

[End of Survey Debriefing Statement]

A FINAL THANKS & DISCLOSURE...

Thanks again for helping us evaluate LezParlay! Before you go we wanted to give you some more information about the detailed results you received in the LezParlay as an Official Tester. In addition to getting your feedback and ideas for the next version of the competition, another goal of this study was to evaluate whether delivering results for health-related topics in LezParlay had any benefits for players' health and well-being. To fully examine this, we had to make sure that balanced groups of Official Testers received more and less health-related feedback.

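### The average-quantity item is asked per time in Rounds 3 and 7 but per day, over a different look-back, in the final survey

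*Protocol*

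**What the plan says.** Appendix C prints one alcohol block under the heading "Alcohol Use Questions (Round 3 & Replay Bonus in Round 7". It holds four items with a two-month look-back:

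- frequency: "on average, how many days per week did the Typical Lesbian drink alcohol"
- average quantity: "on average, how many drinks did the Typical Lesbian have each time she drank"
- peak: drinks on the heaviest day
- consequences: a count out of eight.

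These are the norm versions. The self-report versions are not printed, but Appendix C states: "Parallel Questions will also ask participants to report their own corresponding behavior/attitude/experience".

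Section 3 (Procedures) makes Round 3 the baseline of the randomised evaluation and the Round 7 replay answers its two-month follow-up.

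The Appendix D survey, given after the competition ends, says "please answer the 5 drinking questions a final time". Its quantity item asks for the average number of drinks "HAD EACH DAY YOU DRANK", and all its drinking items count from the start of July.

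On entry, inclusion criterion 1 in section 2 (Subject Recruitment) refers to a single occasion for the drink count and, for frequency, to "drinking alcohol 3+ times per week during the past 2 months". Section 3 says the Round 3 screen uses "number of drinking days per week and peak drinks on a single day during the past 2 months", then describes the peak threshold in terms of an occasion.

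**The concern.** The background section sets longitudinal change in alcohol use as the efficacy target. The final survey repeats the drinking items and tells women they are answering the same questions again, so it reads as a third wave of the same measure. For average quantity it is not the same measure: the denominator moves from a time to a day. A woman who sometimes drinks twice in a day would give a higher number in the final survey with no change in her drinking. The look-back also changes, from a fixed two months to a period whose length depends on when she completes the survey.

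There is a second mismatch inside Rounds 3 and 7. Frequency and peak are per day while average quantity is per time, so the three items describe drinking on one scale only if each drinking day holds one occasion. If a woman gave up a second, similar-sized sitting on the days she drinks, neither her days per week nor her per-time average need fall. A per-day average would.

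**Working it through.** The protocol gives no figure that depends on this point, so there is none to reproduce. The check is a comparison of wording, followed by an illustration.

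**1. Items side by side**

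| Item | Rounds 3 and 7 (Appendix C) | Final survey (Appendix D) |
|---|---|---|
| Frequency | days per week | days per week |
| Average quantity | drinks per time | drinks per day |
| Peak | drinks on heaviest day | drinks on heaviest day |
| Consequences | count out of 8 | count out of 8 |
| Look-back | two months | from the start of July |

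Only average quantity changes unit. The look-back changes for every item.

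**2. Relation between the two units.** Let D be total drinks, T the number of separate drinking times and d the number of drinking days in the window. The per-time answer is q = D/T. The per-day answer is D/d = q × (T/d) = kq, where k = T/d is at least 1. The sittings need not be equal in size. The documents give no value for k; the range 1.0 to 1.5 is an assumption.

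**3. Round 3 to Round 7.** Both rounds ask for q. For unchanged drinking the change due to wording is q − q = 0 for any k.

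**4. Round 3 or 7 to the final survey.** For unchanged drinking the apparent change is kq − q = (k − 1)q. With q = 3 (assumed):

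| k | Final-survey answer | Apparent change | Relative |
|---|---|---|---|
| 1.0 | 3.0 | 0 | 0% |
| 1.1 | 3.3 | +0.3 | +10% |
| 1.25 | 3.75 | +0.75 | +25% |
| 1.5 | 4.5 | +1.5 | +50% |

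**5. Within Rounds 3 and 7.** If days per week were multiplied by the per-time answer, the product would fall short of weekly drinks by 1 − 1/k: 0% at k = 1.0, 9.1% at 1.1, 20% at 1.25 and 33.3% at 1.5. The protocol does not define such a product; this only shows how far the items can disagree.

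**6. Between arms.** If k is the same in all arms, a difference of 0.6 with SD 2.0 on the per-time scale (both assumed) becomes 0.6k with SD 2.0k per day. The ratio stays at 0.6k/2.0k = 0.3. With 166 women per arm (500/3, rounded down), illustrative power is 0.780 at k = 1, 1.25 and 1.5. The raw difference does move, to 0.75 at k = 1.25 and 0.90 at k = 1.5, so raw estimates from Round 7 and the final survey are not in the same unit.

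**7. Entry wording.** Two drinking days per week are 2k = 2.0 to 3.0 times per week. Read literally, the two frequency rules can differ for the same woman at the top of that range.

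**The case against.** The case against giving this much weight is strong, and most of it stands.

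- A reader might infer that the drinking outcome has no fixed unit, or that the trial's main change score sits on two scales. The documents do not support that. Baseline and the designated follow-up share one printed item set, and frequency and peak keep their unit throughout.
- A reader might infer a biased treatment effect. A wording shift common to all arms does not create an arm difference.
- A reader might infer that a weekly-volume outcome is understated. The protocol defines no such outcome.
- A reader might infer that women will be wrongly enrolled. No times-per-week item is printed. The printed Round 3 items measure days per week and the peak day, and section 3 screens on those. Criterion 1 is loose prose beside them, not a second instrument.
- A reader might infer that a drink is never defined. The self-report screens are not printed and some app screens are missing from the text, so this cannot be judged. Such a gap would in any case be constant across waves.
- The quantity item stands between two per-day items, so many women may read it as per drinking day. The effect could be close to nil.
- The protocol does not say how the survey's drinking answers enter the efficacy analysis; that may be settled in an analysis plan not shown.

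What the objection does not remove is the mismatch itself. The survey presents a changed item as a repeat. It is also not clearly peripheral: Appendix C assigns the coping block to Round 4 only, so the only later drinking-to-cope item printed is in this survey. An analysis plan can choose whether to use that wave, but it cannot recover k after the answers are collected.

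**Conclusion.** The point holds in a limited form. Average quantity is per time in Rounds 3 and 7 and per day in the final survey, with a different look-back, although it is presented as the same question. The Round 3 to Round 7 contrast is unaffected, and no systematic arm bias follows. Any quantity change or trajectory that includes the final survey mixes units, and the Round 3 and Round 7 quantity item does not match its per-day neighbours if a drinking day can hold more than one occasion.

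The size is unknown: 0% to 50% under the assumed k of 1.0 to 1.5, and zero at k = 1. The conclusion also assumes that the unprinted self-report items follow the printed norm wording, as Appendix C says they will. This is a nearly free improvement to the instrument, not a threat to the designated comparison. The entry wording is a secondary matter of consistency and does not alter the scale of the outcome.

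**What to change.** Before launch:

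1. Word the quantity item in Rounds 3 and 7, in both its own and norm versions, as drinks on each day the woman drank. This matches the frequency and peak items and the final survey.
2. Give the final survey the same two-month look-back, or state how long its window is. This matters for peak and consequences too, since a maximum and a count both tend to grow with the length of the window.
3. As a secondary edit, reconcile inclusion criterion 1 in section 2 with the screening answers in section 3 and the Appendix C items, so that all three use the same terms.

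The cost is a few words in the item text and one criterion. No procedure, sample size or visit changes.
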